## **6.3 Interim Analysis**

Interim analysis during this study shall be conducted at Day 7, 14 and 21 for the 70 participants to ensure participant safety before the other participants enter into the trial.

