### **8.10 Treatment Compliance**

Compliance is assessed by counting the number of returned bottles if any at each visit. The Investigator (or delegate) must complete the appropriate pages of the treatment log form and of the CRF. A discontinuation is defined as a period with a least three consecutive days without study medical device intake.

The study shall be open enrollment but patients must have access to the clinical location for clinical survey reporting. The survey must be completed two (2) times per week during the 21 day long trial. Potential participants should reside in the United States.

The monitor supervising the study will verify the data by comparing the recorded data with the investigational product retrieved.

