### **8.11 Participant Reimbursement**

Participants shall be reimbursed at a rate of seven dollars (\$7.00) per day for each day that data for the two objectives is sent to the Principal Investigator. The reimbursement is provided for the participant's time for recording the data on a personal smart device, the cost of data transfer and overall phone costs for sending the information to the Principal Investigator. The total reimbursement amount that may be provided to the participant is no more than \$210.00. The reimbursement shall be provided to the participant, by the Sponsor, after the participant completes the trial period by company check paid to the participant.

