#### **9.1.1.1 Primary Criterion**

Composite success rate. Safety - no issues or reported adverse conditions.

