#### **9.1.1.2 Secondary Criterion**

Percent change of spirometer reading from before treatment compared to three (3) hours after treatment by the participant. Subjective participant opinion of the efficacy provided by semi-weekly surveys.

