## **12.3 Description by Type of Visit**

- Baseline enrollment form completed and submitted online (secure site), informed consent signed and submitted.
- Follow up call, email and follow up summary completed by the Investigator at the end of the one month treatment period with written results.
- Three (3) month participant courtesy email to confirm safety and answer any questions.

**There is no strict timing for the phone calls. In any case, it is better to call the patient after a delay, than to not call them at all (even in this case, the phone call record page of the CRF should be completed).**

The patient visit schedules will be given by the Investigator as soon as the participant is randomized, so as the Investigator can plan in advance all the necessary appointments with the participant.

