#### **13.7.1.1 Description of the Primary Variable(s)**

The primary efficacy endpoint is the composite cluster of the first occurrence, over the duration of study (randomization to study end date inclusive), of the following adjudicated events:

- Any skin conditions caused by the device to include irritations,
- Any allergic reactions,
- Any new medical conditions during the study.

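### No contact described for the 21-day device period is stated to ask participants about harms, although the safety criterion, the counted endpoint and the safety looks all depend on harms being reported.

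*Protocol*

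**What the plan says.** **Results that depend on harms being reported.** Protocol 9.1.1.1 defines a composite success rate whose safety part reads "Safety - no issues or reported adverse conditions". Section 13.7.1.1 defines the primary endpoint as the first adjudicated event from a list that begins "Any skin conditions caused by the device to include irritations" and continues with allergic reactions and new medical conditions. Section 13.7.1.2.3 analyses it as the proportion event-free over time. Section 6.3 adds safety looks: "Interim analysis during this study shall be conducted at Day 7, 14 and 21 for the 70 participants to ensure participant safety".

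**Contacts during device use.** Section 8.10 sets the survey frequency: "The survey must be completed two (2) times per week during the 21 day long trial". It adds that "patients must have access to the clinical location for clinical survey reporting". The only content stated for the survey is in 9.1.1.2: "Subjective participant opinion of the efficacy provided by semi-weekly surveys". Section 9.1.2 lists the surveys as a secondary clinical assessment method. Section 8.11 pays participants "for each day that data for the two objectives is sent to the Principal Investigator"; under 5.1 and 5.2 those objectives are measured by pulse oximetry and spirometry. Section 8.10 also refers to visits, in connection with compliance.

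**Contacts afterwards.** Section 12.3 lists "Follow up call, email and follow up summary completed by the Investigator at the end of the one month treatment period with written results", says that calls have no strict timing, and ends with a three-month courtesy email, one purpose of which is to confirm safety.

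**Recording rule.** Section 10.1 requires all adverse events to be entered on the CRF, with onset, intensity, action, outcome and causality. It names no method or timing for eliciting them. The SAP says nothing on collection.

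**The concern.** Mild skin and allergic events are the kind that participants may not mention unless asked, and they are the events that 13.7.1.1 counts. If the contacts are run as described, participants are asked about efficacy and send efficacy measurements while using the device, and nothing assures that they are asked about harm. An event that is never recorded counts as a success.

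Nothing later in the plan recovers it. The Clinical Events Committee reviews only reported events (6.4, Appendix 4). A participant with no recorded event is censored as event-free (13.7.1.2.1). Missing values are not imputed (13.4.2.1). With one arm there is no comparison group against which to judge reporting, so any shortfall falls directly on the reported proportion. An empty Day 7 or Day 14 look could mean no harm, or that nobody asked.

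**Working it through.** **1. The plan's own figure.** The only relevant planning number is 70 participants (13.2). It cannot be reproduced, because no event rate, effect, standard deviation, power or dropout is given. No adverse event rate, recording rate or success threshold is stated either.

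**2. The described contacts side by side.**

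| Contact (Protocol section) | Timing | Stated content | Harm question stated? |
|---|---|---|---|
| Survey (8.10, 9.1.1.2, 9.1.2) | 2 per week × 3 weeks = 6 | Opinion of efficacy | No |
| Data sent to investigator (8.11) | Up to daily | Oximetry, spirometry | No |
| Visits (8.10) | Not listed | Compliance count | No |
| Call, email, summary (12.3) | End of one month | Written results | No |
| Courtesy email (12.3) | Month 3 | Confirm safety | Safety purpose, but after device use |

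The Day 7, 14 and 21 looks (6.3) are analyses, not contacts, and their data source is not named. Vital signs are taken before enrolment (13.8.3), so they do not fill the gap.

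The length of the period is itself inconsistent. The cap in 8.11 gives $210 / $7 = 30 paid days, whereas 21 days would give 21 × $7 = $147; 12.3 speaks of one month. If the month is 30 days, the end-of-treatment contact falls 30 − 21 = 9 days after Day 21. These passages must be reconciled.

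**3. Direction and illustrative size.** Let p be the true proportion of participants with an event and s the share of them whose event is recorded. Both are assumptions. False reports are taken as nil.

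- Observed event-free proportion = 1 − p·s
- Overstatement = (1 − p·s) − (1 − p) = p(1 − s)
- Expected number recorded = 70·p·s
- Probability that none is recorded = (1 − p·s)^70

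| p | s | True event-free | Observed | Overstatement (points) | Recorded of expected | P(none recorded) |
|---|---|---|---|---|---|---|
| 5% | 80% | 95% | 96% | 1 | 2.8 of 3.5 | 0.057 |
| 5% | 50% | 95% | 97.5% | 2.5 | 1.8 of 3.5 | 0.170 |
| 5% | 30% | 95% | 98.5% | 3.5 | 1.1 of 3.5 | 0.347 |
| 10% | 80% | 90% | 92% | 2 | 5.6 of 7.0 | 0.003 |
| 10% | 50% | 90% | 95% | 5 | 3.5 of 7.0 | 0.028 |
| 10% | 30% | 90% | 97% | 7 | 2.1 of 7.0 | 0.119 |
| 20% | 50% | 80% | 90% | 10 | 7.0 of 14.0 | 0.001 |
| 30% | 50% | 70% | 85% | 15 | 10.5 of 21.0 | <0.001 |

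With full recording (s = 1) the overstatement is zero, and P(none recorded) is 0.028 at p = 5% and 0.0006 at p = 10%.

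**4. What a clean result would mean.** With 0 of 70 recorded, the upper limit of an exact two-sided 95% interval is 1 − 0.025^(1/70) = 5.1%. That limit applies to recorded events. At s = 50% the corresponding limit for true incidence is 5.13% / 0.5 = 10.3%.

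**The case against.** A reader might infer more: that the survey is the only scheduled contact, that harms are counted only if volunteered, and that the result is therefore biased. The documents do not support this.

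- **Other contacts exist.** Participants may send data daily (8.11), visits are mentioned (8.10), appointments are to be planned (12.3), and 11.2 refers to a study flowchart that is not in the text available. Its content is unknown.
- **The survey form is not in the documents.** Section 9.1.1.2 says what the survey contributes to an efficacy criterion, which need not be all that it asks. Section 8.10 speaks of clinical survey reporting.
- **Recording is mandatory.** Section 10.1 covers all adverse events, and 11.1 and 11.2 require continued safety follow-up. Silence on how events are elicited does not show that only spontaneous reports are used.
- **The safety criterion is not purely report-based.** It also names issues, which an investigator could observe.
- **The recording shares are assumed.** The arithmetic shows what a given shortfall would do, not that there is one.
- **The primary endpoint is unsettled.** Section 5.1 points to oximetry, 9.1.1 to spirometry and oximetry, 13.7.1 to the appearance of cystic fibrosis, and 13.7.1.1 to harms. Whether missed harms change the headline result depends on which one governs.

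All of this stands, and it limits the claim to what is not assured. It does not supply a stated question, checklist or skin check about harms during the 21 days. Nor does the endpoint conflict remove the issue: the safety part of 9.1.1.1, the adverse event percentages in 13.8.1.2 and the looks in 6.3 are affected whichever endpoint governs.

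**Conclusion.** The concern holds as a gap in assured collection. During device use, every participant contact described is for efficacy opinion, oximetry and spirometry data, or compliance, and the one contact with a stated safety purpose comes at month 3. A late answer may still add an event to the final count, but it cannot inform the Day 7, 14 or 21 looks.

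The direction is clear if false reports are negligible: incomplete recording can only raise the event-free proportion and the safety part of success. The size cannot be obtained from the documents. Over the illustrative range with half of the affected participants recorded, the overstatement runs from 2.5 points at 5% incidence to 15 points at 30%. The defensible wording is that these results may be biased towards success, not that they are. It is more than missing detail, because the safety looks as described have no solicited harm data to review.

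**What to change.** **Change.**

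- In 8.10 and 9.1.1.2, state that each twice-weekly survey carries fixed safety questions: skin irritation at the application site, allergic reaction, any new or worse condition, and the onset date of each.
- Send every positive answer to the investigator for assessment and recording, and name the CRF page.
- In 6.3, name these answers as the data source for the Day 7, 14 and 21 looks.
- In 13.8.1.2 and the SAP, report the survey response rate beside every adverse event percentage, so that no event can be told apart from no answer.
- Reconcile 10.3 with 13.7.1.1. The former says that efficacy endpoints are not adverse events and go on outcome event forms; the latter makes harms the primary efficacy endpoint. State the route by which one skin, allergic or new condition reaches both the adverse event tables and the endpoint. Without this, the new questions would feed a contradictory recording rule.

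**Cost.** A few questions on a survey already planned about six times per participant, some investigator time for positive answers, and wording changes in the sections named. More mild events will be recorded, so the safety figure will look less favourable.

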### **9.1.2 Clinical Assessment Methods**

Primary: Measurements of before and after with pulse oximetry device and spirometer.

Secondary: Participant surveys completed.

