### **5. STUDY OBJECTIVES**

#### **5.1 Primary Objective**

To specifically illustrate and measure both clinical and empirical efficacy described by (AARC) in the Clinical Practices Guidelines for Postural Drainage Therapy (1991) for external manipulation of the thorax for postural drainage therapy and the secretion clearance, or presence of atelectasis caused by mucus plugging.

Outcome measured by:

Percentage change of oxygen levels in the blood (pulse oximetry). SpO2 will be monitored using the standard pulse oximeter system (K131111). Change from baseline before treatment and measure again up to 3.5 hours after treatment.

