## **5.2 Secondary Objective**

To observe the quality of lung function that participants experience during the use of the device during the trial period.

Outcome measured by:

Percentage change of lung function. Evaluate expiratory forced vital capacity (FVC) and forced expiratory volume (FEV1) will be monitored with standard spirometer. Change from baseline before treatment and measure again up to 3.5 hours after treatment.

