## **9. ASSESSMENT OF INVESTIGATIONAL PRODUCT**

### **9.1 Efficacy**

The goal of this trial is to illustrate before and post treatment changes measured by spirometer.

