### **9.1.1 Efficacy Criteria**

Primary: Physical exam by medical practitioner for initial diagnosis and changes in spirometer reading from before treatment compared to reading three (3) hours after treatment. In addition, changes in iHealth Air pulse oximeter (FDA 510k K131111) reading from before treatment compared to reading three (3) hours after treatment.

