#### **13.7.1.2.4 Multiple Comparisons/Multiplicity**

If the primary efficacy reaches statistical significance, then the two secondary endpoints will be formally tested at the 5% level in a hierarchical (step-down) procedure.

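### Sections 5 and 9 of the protocol disagree on whether spirometry is primary, and the primary success rate is undefined, so no single primary result can be identified

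*Protocol*

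**What the plan says.** The protocol ranks the two physiological measures in six places:

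- 5.1 (primary objective): "Percentage change of oxygen levels in the blood (pulse oximetry", read up to 3.5 hours after treatment. No other measure is named.
- 5.2 (secondary objective): "Evaluate expiratory forced vital capacity (FVC) and forced expiratory volume (FEV1) will be monitored with standard spirometer", with the same time window.
- 9.1: "The goal of this trial is to illustrate before and post treatment changes measured by spirometer".
- 9.1.1: "Primary: Physical exam by medical practitioner for initial diagnosis and changes in spirometer reading from before treatment compared to reading three (3) hours after treatment". The next sentence adds the oximeter change at three hours.
- 9.1.1.2 (secondary criterion): "Percent change of spirometer reading from before treatment compared to three (3) hours after treatment by the participant", together with the participant's opinion from the surveys.
- 9.1.2: "Primary: Measurements of before and after with pulse oximetry device and spirometer". Only the surveys are left as secondary.

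The primary criterion itself, in 9.1.1.1, reads "Composite success rate. Safety - no issues or reported adverse conditions". Section 9.1.2.1, headed as the definition of the components of the primary endpoint, is marked not applicable.

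Section 13.7 does not settle the matter. Its primary variable is a reduction in the appearance of cystic fibrosis (13.7 and 13.7.1). It is then a cluster of skin, allergic and new medical events (13.7.1.1), analysed by a log-rank test at 0.05 (13.7.1.2.3). SpO2, FEV1 and FVC do not appear there. The SAP sets a two-sided 5% level and names no endpoint.

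**The concern.** A primary endpoint has to be one named variable, with a time point, a definition of success and a test, all fixed before the data are seen. Here the same three-hour spirometer change is primary in 9.1.1 and secondary in 9.1.1.2, two subsections later. SpO2 is the sole primary outcome in one place and shares the position in two others. The success rate that is called the primary criterion cannot be computed from the readings.

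At stake is what a positive result would mean. The sponsor intends the trial to support a request for a new reimbursement code. As written, a report could present SpO2, FEV1, FVC or a responder rate with cut-offs chosen afterwards as the primary result, and each could point to a section that supports it.

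**Working it through.** **Step 1. Rank of each measure, side by side.**

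| Section | SpO2 | Spirometry | Survey | Timing |
|---|---|---|---|---|
| 5.1 / 5.2 | primary | secondary (FVC, FEV1) | not mentioned | up to 3.5 h |
| 9.1 | not mentioned | goal of the trial | not mentioned | not given |
| 9.1.1 | primary | primary | not mentioned | 3 h |
| 9.1.1.2 | not mentioned | secondary | secondary | 3 h |
| 9.1.2 | primary | primary | secondary | before and after |

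Spirometry is primary in 9.1.1 and 9.1.2 and secondary in 5.2 and 9.1.1.2. Section 9.1 does not use the word primary, and the conflict stands without it. The set of secondaries also changes: FVC and FEV1 in 5.2, spirometry and survey in 9.1.1.2, survey alone in 9.1.2.

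**Step 2. Can the composite success rate be computed?** It would need components, a cut-off for each, and a rule (any or all). No SpO2, FEV1 or FVC cut-off and no such rule appears in the protocol or the SAP.

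**Step 3. Is a test assigned to any marker?** No. The only named test is the log-rank test on the event cluster. That test compares groups, and 8.3 places everyone in a single arm.

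**Step 4. Size, conditional on how the freedom is used.** The level (two-sided 0.05) comes from 13.7.1.2.3 and the SAP. The documents give no correlations between markers, so those below are assumptions. The device is taken to have no effect.

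*Success on any one of three markers, independent:*
- Either direction: 1 − 0.95³ = 1 − 0.8574 = 14.3%.
- Favourable direction only: 1 − 0.975³ = 1 − 0.9269 = 7.3%.

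*Success on any one of three, correlated* (simulated trivariate normal statistics):

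| SpO2 with each | FEV1 with FVC | Either direction | Favourable |
|---|---|---|---|
| 0 | 0.8 | 12.4% | 6.3% |
| 0.3 | 0.8 | 12.1% | 6.1% |
| 0.3 | 0.9 | 11.4% | 5.7% |
| 0.5 | 0.9 | 10.9% | 5.4% |
| 0.7 | 0.95 | 9.5% | 4.7% |

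One fixed marker gives 5% and 2.5%.

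*Success only if all three are significant:* the favourable false-positive chance cannot exceed that of a single marker, 2.5%. With one-sample t-tests at n = 70, it is about 0.1% when SpO2 correlates 0.2 with each spirometry measure and FEV1 correlates 0.8 with FVC. It is about 0.3% when the first correlation is 0.5.

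**The case against.** Four arguments limit the point.

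**The text may mean that both are required.** Section 9.1.2 joins oximeter and spirometer with a plain conjunction, and 9.1.1 adds oximetry to spirometry. A co-primary reading is at least as natural as either/or, and it would lower the false-positive chance. This stands: the documents state no rule, so the inflated figures are conditional and are not a property of the plan.

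**The step-down already controls error.** A reader might infer the opposite, that spirometry serves both as the gate and as a gated test, because 13.7.1.2.4 says that after a significant primary "then the two secondary endpoints will be formally tested at the 5% level in a hierarchical (step-down) procedure". The documents do not show that. The rule sits in 13.7, where the primary is the event cluster and the secondary is another cluster (13.7.2.1) whose events are not listed. As written it neither gates spirometry nor protects it.

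**The composite may be defined in 13.7.1.1.** Section 9.1.1.1 pairs the success rate with freedom from adverse conditions, so success could mean staying free of the listed events. That is possible, but no passage links the two. The list contains harms and says nothing about SpO2 or lung function. It adds a competing primary endpoint and leaves the gap open.

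**Section 9.1 makes spirometry primary.** It does not go that far: it states a goal and gives no rank. It should be aligned, but it is weaker evidence than 9.1.1 and 9.1.2.

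**Conclusion.** The point holds as an inconsistency in current text. Sections 5 and 9 give spirometry two ranks, the primary success rate has no computable definition, and no test is attached to SpO2, FEV1 or FVC. The primary result therefore cannot be identified in advance.

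The numerical consequence is conditional. With an any-of-three rule and no device effect, the chance of a false claim is roughly two to three times nominal: 9.5% to 14.3% against 5%, or 4.7% to 7.3% against 2.5% in the favourable direction. The range rests on assumed correlations. With an all-three rule there is no inflation. A reader should not conclude that the trial has a 14% error rate or that the sponsor intends to choose among markers. The documents support only that they leave the choice open.

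**What to change.** 1. Name one primary marker and use it throughout. The hierarchy already in section 5 (SpO2 change primary, spirometry secondary) is the natural default, though the choice is the sponsor's. With that choice, take spirometry out of the primary lists in 9.1.1 and 9.1.2 and align the goal sentence in 9.1.
2. Delete the composite success rate from 9.1.1.1 and move the statement on adverse conditions to the safety section.
3. Carry the same primary variable into 13.7 and the SAP, with a paired before/after test in place of the log-rank test. Correcting section 9 alone would leave a different primary endpoint in the statistics section.
4. Fix one post-treatment time point, reconciling the window of up to 3.5 hours in 5.1 and 5.2 with the three hours in 9.1.1 and 9.1.1.2.
5. State which two secondaries enter the step-down in 13.7.1.2.4 and in what order, before any data are seen. FEV1 and FVC, with the survey as an other endpoint, is one option. The documents do not settle the order or the survey's place: 5.2 gives no test order, and 9.1.1.2 and 9.1.2 both list the survey as secondary.

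The cost is a wording amendment to the protocol and SAP, with no new data. The downside is that primary success could no longer be claimed on spirometry alone.

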#### **9.1.2.1 Definitions of Components of the Primary Efficacy Endpoint**

N/A

## **10. PATIENT SAFETY**

### **10.1 Adverse Events Monitoring**

#### **Definitions:**

An adverse event is any untoward medical occurrence in a clinical investigation participant administered a medical device and which does not necessarily have to have a causal relationship with this treatment.

A Serious Adverse Event is any untoward medical occurrence at any dose that:

- Results in death or;
- Is life-threatening or;  
Note: The term "life-threatening" in the definition of "serious" refers to an event in which the patient was at risk of death at the time of the event; it does not refer to an event that hypothetically might have caused death if it were more severe.
- Requires inpatient hospitalization or prolongation of existing hospitalization or;
- Results in persistent or significant disability/incapacity or;
- Is a congenital anomaly/birth defect;
- Is a medically important event:  
Medical and scientific judgment should be exercised in deciding whether expedited reporting is appropriate in other situations, such as important medical events that may not be immediately life-threatening or result in death or hospitalization but may jeopardize the patient or may require intervention to prevent one of the other outcomes listed in the definition above. These should also usually be considered serious.

